1.2 SCHEMA

[figure not shown]
Visit 0  
Introductory  
Visit

Obtain informed consent, screen for participant eligibility, obtain measures of height, weight, ECG, blood pressure, and heart rate. Measure maximal aerobic capacity via VO2 max test.

[figure not shown]
Visit 1  
Exercise  
Control Visit

[figure not shown]
Visit 2-5  
Phase I  
Cannabis  
Visits

Visits 2-5  
Phase I  
Cannabis +  
Exercise  
Visits

Visit 6-9  
Phase II  
Cannabis  
Visits

Visit 6-9  
Phase II  
Cannabis +  
Exercise  
Visits

[figure not shown]

Figure 1. Schematic breakdown of study structure, and schedule of measures.

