### 1.3 SCHEDULE OF ACTIVITIES (SOA)

Procedure	Introductory Visit (Visit 0), Day 0	Exercise Control Visit (Visit 1), Day 7±1 day	Phase I Cannabis Visit (Visit 2), Day 14±1 day	Phase I Cannabis + Exercise Visit (Visit 3), Day 21±1 day	Phase I Cannabis Visit (Visit 4), Day 28±1 day	Phase I Cannabis + Exercise Visit (Visit 5), Day 35±1 day	Phase II Cannabis Visit (Visit 6), Day 42±1 day	Phase II Cannabis + Exercise Visit (Visit 7), Day 49±1 day	Phase II Cannabis Visit (Visit 8), Day 56±1 day	Phase II Cannabis + Exercise Visit (Visit 9), Day 63±1 day
Informed Consent	X									
Eligibility Questionnaire	X									
Physical Activity Readiness Questionnaire	X									
Height	X									
Weight	X	X	X	X	X	X	X	X	X	X
Blood Pressure and Heart Rate	X	X	X	X	X	X	X	X	X	X
Urine Test	X	X	X	X	X	X	X	X	X	X
Inquiry of Changes to Health and Prescription Status		X	X	X	X	X	X	X	X	X
VO 2 Max Test	X									
Pulse Wave Velocity		X	X	X	X	X	X	X	X	X
Brachial Artery FMD		X	X	X	X	X	X	X	X	X
Echocardiography		X	X	X	X	X	X	X	X	X
20 Minute Maximal Cycling Exercise		X		X		X		X		X
Vaporization of High THC Cannabis			X	X				X	X	
Smoking of High THC Cannabis					X	X				
Vaporization of High CBD Cannabis							X			X
Indirect Calorimetry/CPET	X	X		X		X		X		X
Microneurography (MSNA)			X							
Stress Echocardiography			X		X		X		X	
Measurement of Continuous Blood Pressure		X	X	X	X	X	X	X	X	X
ECG	X	X	X	X	X	X	X	X	X	X
Impedance Cardiography		X		X		X		X		X
Drug Effects Questionnaire			X	X	X	X	X	X	X	X

*This study will use a randomized crossover design. Phase I of this study will occur prior to the initiation of phase II. If a participant enters the study in phase II, but did not participate in phase I, they will be required to complete the introductory and exercise control visits. Visits 2-5 and 6-9 will occur in a randomized order, which will be individualized for each participant.*

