## 4 STUDY DESIGN

### 4.1 OVERALL DESIGN

The study will use a randomized cross-over design. It will be structured by division into two phases. Both phases will examine the acute cardiovascular response to cannabis consumption,

both at rest and during exercise. *Phase I* will examine if and how this response differs whether cannabis is smoked or vaporized. *Phase II* will examine how this response is influenced by cannabinoid concentration within inhaled cannabis. Phase II of the current study will use a single-blind design, with participants being unaware of the relative cannabinoid concentrations of the cannabis they consume. Cannabis will be inhaled using methods of smoking (phase I only) or vaporization (phase I and II). Each experimental study visit (study visits 2-9), 100mg of cannabis will be consumed via one of the two aforementioned methods of inhalation, followed by a subsequent rest period, or by 20 minutes of exercise. Primary endpoints will be examined pre- and post-consumption each visit (with the exception of muscle sympathetic nerve activity, which will only be performed on a single study visit), while secondary endpoints will be recorded during exercise.

Each phase of the study will require participants to complete an introductory and control visit, as well as 4 experimental study visits, where cannabis inhaled under alternating conditions (phase I: smoking vs. vaporizing high THC cannabis, phase II: high CBD cannabis vs. high THC cannabis) followed by exercise, or a time-matched rest period. The order in which these visits will occur will be randomized, and individualized for each participant. A within-subjects design will be utilized, so that each participant completes each condition. High THC cannabis used will be the cannabis strain “Rex”, while the high CBD strain will be “Kalea”. The dose size and strength will not be altered throughout the course of the study.

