### 8.3.4 TIME PERIOD AND FREQUENCY FOR EVENT ASSESSMENT AND FOLLOW-UP

The occurrence of an adverse event or serious adverse event may come to the attention of study personnel during study visits and interviews of a study participant. Participants will be told in the initial study visit that they should report any adverse events they are experiencing after completing any study procedures.

All adverse events including local and systemic reactions not meeting the criteria for serious adverse events will be captured on the adverse event form. Information to be collected includes event description, time of onset, assessment of severity, relationship to study product (assessed by an investigator), and time of resolution/stabilization of the event. All adverse events occurring while in the study must be documented appropriately regardless of relationship. All adverse events will be followed to adequate resolution.

Any medical condition that is present at the time that the participant is screened will be considered as baseline and not reported as an adverse event. However, if the study participant's condition deteriorates at any time during the study, it will be recorded as an adverse event.

---

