## 9.3 POPULATIONS FOR ANALYSES

Only participants who complete all study procedures will be included for analysis of efficacy endpoints. All participants who consume cannabis at any time will be included in the analysis of safety endpoints.

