#### 9.4.4 SAFETY ANALYSES

Safety analysis will be performed using summary statistics during treatment interventions. Adverse events will be coded according to the Medical Dictionary for Regulatory Activities and will have severity, and relationship of adverse event to study intervention presented by System Organ Class and preferred term groupings. Each instance of an adverse event will be presented as a discrete event. Duration of events, severity, relationship to intervention, expectation, and outcome will be presented. Adverse events that lead to premature discontinuation will be presented in a table, along with all treatment-emergent serious adverse events.

---

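### The safety set is defined by cannabis consumption, but the maximal exercise control and the VO2 max test come before any dose, so events there in people never dosed fall outside it

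*Protocol*

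**What the plan says.** Protocol 9.3 and SAP section 3 use the same two sentences. For safety: "All participants who consume cannabis at any time will be included in the analysis of safety endpoints". For efficacy: "Only participants who complete all study procedures will be included for analysis of efficacy endpoints". No third population is defined.

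The schedule of activities (Protocol 1.3) marks "20 Minute Maximal Cycling Exercise" at Visit 1. The schema (1.2) places a maximal test at Visit 0: "Measure maximal aerobic capacity via VO 2 max test". Cannabis starts later. Section 4.1 says "Each experimental study visit (study visits 2-9), 100mg of cannabis will be consumed via one of the two aforementioned methods of inhalation", and 1.3 confines randomization to the later visits: "Visits 2-5 and 6-9 will occur in a randomized order, which will be individualized for each participant".

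On recording, Protocol 8.3.4 is broad: "All adverse events occurring while in the study must be documented appropriately regardless of relationship". On reporting, Protocol 9.4.4 and the matching SAP section restrict the safety summaries to the treatment interventions and add "Each instance of an adverse event will be presented as a discrete event". They also promise a table of events that led to premature discontinuation, shown with the treatment-emergent serious events. No population is named for that table.

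**The concern.** A safety set limited to dosed participants is the usual choice when the drug is the only exposure of interest. Here it is not. Exercise without cannabis is listed in Protocol 9.4.1 as one of the conditions in both phases, and it is delivered as a maximal effort. The rule for collecting events covers everything that happens in the study, while the rule for analysing them starts at the first dose.

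At stake is whether the safety report says what happened to everyone who underwent the exercise control. If the stated rule is followed literally, Visit 1 events are summarised only in people who went on to be dosed. A person stopped by an event at that visit is the one most relevant to the safety of exercise alone, and is the one left out. Section 7.2 has such a person replaced, so a full complement of completers would not reveal the gap. In a trial of 20 people per phase, one serious event placed outside the safety tables would matter to a reader.

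**Working it through.** The plan states no figure to reproduce. The check sets the schedule beside the population definitions.

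**Step 1: order of exposure.**

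| Visit | Maximal effort | Study cannabis | Source |
|---|---|---|---|
| 0 | VO2 max test | none | Protocol 1.2, 1.3 |
| 1 | 20-minute cycling control | none | Protocol 1.3 |
| 2–5 (phase I) | at two of the four visits | every visit | Protocol 1.3, 4.1 |
| 6–9 (phase II) | at two of the four visits | every visit | Protocol 1.3, 4.1 |

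Order is randomized only within Visits 2–5 and within Visits 6–9, so Visits 0 and 1 stay first. The footnote in 1.3 requires someone who enters directly in phase II to complete them too.

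**Step 2: how much of the exercise is before dosing.** One-phase participant: 1 (VO2 max) + 1 (control) + 2 (cannabis plus exercise) = 4 maximal efforts, 2 of them before any dose. Two-phase participant who does Visits 0 and 1 once: 1 + 1 + 2 + 2 = 6, again 2 before any dose.

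**Step 3: apply 9.3 to a participant withdrawn after an event at Visit 0 or 1.**
- Efficacy set: not met, because the procedures are incomplete.
- Safety set: not met, because no study cannabis has been consumed. (I read the definition as study cannabis. Inclusion criterion 5 makes every entrant a regular user, so otherwise the definition would select nobody out.)
- Someone already dosed in phase I who repeated Visits 0 and 1 for phase II would be in the set. The gap concerns people not yet dosed.

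**Step 4: does anything else bring the event in?**
- 8.3.4: the event is documented. Capture is not the problem.
- 9.4.4, discontinuation table: it carries no dosing condition and could list the event, but nothing says it reaches beyond the 9.3 set.
- 9.4.4, treatment-emergent serious events: on the usual meaning, a Visit 0 event is not treatment-emergent. Whether a Visit 1 event is depends on whether the exercise control counts as a treatment intervention, which is not stated.
- 9.4.4, layout: grouping is by organ class and preferred term. Neither the condition of onset nor the number who started it is required.

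**Step 5: scale.** The documents give no rate of pre-dose events that lead to withdrawal. To show only how easily the gap could be met, assume a per-person risk *p* and compute 1 − (1 − *p*)^*n*, with *n* = 20 (recruitment per phase, 9.2) or *n* = 40 (two phases, no overlap).

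| Assumed *p* | *n* = 20 | *n* = 40 |
|---|---|---|
| 1% | 1 − 0.99^20 = 18% | 1 − 0.99^40 = 33% |
| 2% | 1 − 0.98^20 = 33% | 1 − 0.98^40 = 55% |
| 5% | 1 − 0.95^20 = 64% | 1 − 0.95^40 = 87% |

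These are chances that at least one person falls outside the set under an invented *p*. They do not estimate how often it will happen.

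**The case against.** The case for leaving the plan alone has several parts, and some of them stand.

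- **The wording guarantees inclusion without excluding anyone.** The safety sentence begins with all, the efficacy sentence with only. True, but it is the sole definition of the safety set, and an analyst following it would build the set from dosed participants.
- **The discontinuation table covers this very case.** It may. A reader could therefore go too far in inferring that anyone harmed at Visit 0 or 1 is certain to vanish from the results. The documents do not support that: the event is on the adverse event form, the reason for withdrawal is recorded under 7.2, and the table might show it. What stands is that 9.3 and 9.4.4 do not fit together.
- **No adverse event comparison is planned, so nothing can be biased.** This stands. A reader might infer that the plan biases the comparison of exercise with and without cannabis, or that it would report, say, 0 of 20 where 1 of 21 is right. The condition list in 9.4.1 belongs to the model for the primary endpoints. Safety is descriptive, and 9.4.4 commits to no proportion by condition.
- **Visit 0 is screening.** This stands. The VO2 max test is not an analysed condition, so the argument is strongest for Visit 1.
- **The protocol's adverse event definition presupposes a product.** Section 8.3.1 does speak of a subject given a pharmaceutical product, but 8.3.4 asks for every event in the study whatever its relationship, and has participants report after any procedure.
- **Events can already be placed by condition.** Onset time is on the form and data are held by visit (9.4.8), so this is possible. It is not planned.
- **Widening the set does not make the conditions comparable.** This stands. Only people who got through Visits 0 and 1 reach the cannabis conditions.

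**Conclusion.** The point holds as a gap in the safety population and its tables. Under the stated rule, a participant withdrawn before dosing because of an event at the exercise control or the VO2 max test belongs to neither analysis set, although exercise alone is a study condition and the event itself is recorded. The result would be incomplete descriptive safety results for exercise alone. The primary and secondary endpoint analyses are unaffected, no planned estimate is biased, and the size cannot be given because the documents contain no event rate.

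This rests on three readings: that the safety sentence means study cannabis; that the 9.3 definition governs the tables in 9.4.4 unless they say otherwise; and that Visits 0 and 1 always come first, as 1.3 shows. If the sponsor already intends the discontinuation table to cover everyone enrolled, saying so would close part of the gap. It would not supply the number of participants who started each condition. The change is worth making before the safety analysis.

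**What to change.** - **Protocol 9.3 and SAP section 3:** define the safety set as all participants who start any study procedure. Keep the dosed participants as a named subset for cannabis-emergent events. State how this fits with 5.4, under which only the reason for ineligibility is kept for screen failures.
- **Protocol 9.4.4 and the SAP safety analyses section:** state that the discontinuation table uses the wider set. Assign each event to the visit or condition in which it began. Beside the event listing, show the number of participants with at least one event over the number who started that condition, for the exercise control and each cannabis condition. List Visit 0 events separately.
- **Report:** note that the cannabis conditions contain only people who got through Visits 0 and 1, so any reading across conditions is descriptive.

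Cost: one extra table and slightly broader safety wording in both documents. The adverse event form already collects time of onset, so no new visit, measurement or participant is needed and no clinical rule changes.

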## 9.4 STATISTICAL ANALYSES

### 9.4.1 GENERAL APPROACH

Our study will be divided into two phases each of which will be analyzed independently. All tests of significance will be two-tailed, and statistical significance will be based upon an alpha error probability of 5% and a power for 80%. The data will be evaluated using both parametric and non-parametric tests, as applicable. If the data are found to be not normally distributed, the raw data will be transformed using an appropriate transformation model in order to perform the parametric assessments. Non-parametric tests will be performed on raw data. The data will be assessed as continuous and will be presented as means with standard deviations. A one-way analysis of covariance will be used to assess the treatment

effects (Phase I: exercise, vaporizing THC, smoking THC, vaporizing + exercise THC, smoking THC + Exercise, Phase II: exercise, vaporizing THC, vaporizing CBD, vaporizing + exercise THC, Vaporizing CBD + Exercise) on the primary endpoints. Covariates will be introduced into the models in order to assess the impact of certain potential factors on outcome, including fitness, blood pressure, resting heart rate, and any other factors that are observed during the study that appear to potentially influence the outcome.

Our secondary endpoints will be assessed using a repeated measures one-way ANOVA and paired t-tests. If there are significant interactions differences between pairs of means will be determined with a Bonferroni post-hoc test.

---

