#### 9.4.3 ANALYSIS OF THE SECONDARY ENDPOINT(S)

Analysis of secondary endpoints will be independent of analysis of primary endpoints. All secondary endpoints will be measured as continuous variables and will be reported as adjusted means with standard deviations. Repeated measures one-way ANOVA and paired Student's *t*-tests will be used for analyses. If there are significant interactions differences between pairs of means will be determined with a Bonferroni *post-hoc* test. Missing data will be imputed using mean imputation from all other measurements collected from the given participant. Outliers will be included and excluded in independent analysis, both of which will be reported.

---

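### The Bonferroni step for secondary endpoints depends on an interaction that the specified one-way model does not contain, and the role of the paired t-tests is undefined

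*Protocol*

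**What the plan says.** Protocol 9.4.1 (General Approach) states: "Our secondary endpoints will be assessed using a repeated measures one-way ANOVA and paired t-tests". The next sentence sets the condition for multiple comparisons: "If there are significant interactions differences between pairs of means will be determined with a Bonferroni post-hoc test". Protocol 9.4.3 (secondary endpoints) repeats both parts: "Repeated measures one-way ANOVA and paired Student's *t*-tests will be used for analyses", then "If there are significant interactions differences between pairs of means will be determined with a Bonferroni" post-hoc test. The matching SAP sections on the general approach and on secondary endpoints carry the same text.

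On error rates, 9.4.1 says "All tests of significance will be two-tailed" and sets alpha at 5%. It defines no family of tests and does not divide alpha.

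The only list of conditions is in 9.4.1, given for the primary endpoints as one set of levels: "Phase I: exercise, vaporizing THC, smoking THC, vaporizing + exercise THC, smoking THC + Exercise". Phase II has a parallel list of five.

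The documents differ on when secondary endpoints are measured. Section 4.1 says "while secondary endpoints will be recorded during exercise". Section 8.1 has blood pressure, heart rate and rate-pressure product recorded in the 20 minutes after inhalation at every visit, at rest or during exercise. In the Schedule of Activities, continuous blood pressure and ECG appear at all of Visits 1-9, while cycling, indirect calorimetry and impedance cardiography appear only at the exercise visits among these.

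**The concern.** The trigger and the model do not fit together. A one-way repeated-measures ANOVA tests one thing, whether the condition means differ. However large that difference, it yields no interaction that could be significant. Taken at its word, the plan gives no route from a significant ANOVA to a Bonferroni comparison.

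The paired t-tests stand beside the ANOVA without a stated purpose. The plan does not say which pairs they compare, whether they wait for a significant F-test, or whether they are adjusted. One analyst could report Bonferroni-adjusted comparisons and another unadjusted t-tests, and both could claim to have followed the plan.

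Ten secondary hypotheses are listed in 9.1, and most predict a direction of change with cannabis, exercise or both, so pairwise tests would carry most of the secondary conclusions. Section 9.4.7 repeats every analysis by sex in identical form, so the ambiguity passes to those analyses too.

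**Working it through.** The plan states no familywise error rate for the secondary endpoints, so there is no figure of its own to reproduce. The check has two parts.

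**1. Can the trigger be met?**

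- Model for secondary endpoints (9.4.1, 9.4.3 and the SAP): one within-subject factor, condition.
- With *k* conditions and *n* participants, the model has one treatment F-test on *k* − 1 and (*k* − 1)(*n* − 1) degrees of freedom. There is no second factor and so no interaction to test.
- Searched for and not found in either document: a two-factor model for any endpoint; a Bonferroni trigger based on the condition effect; an adjustment of the paired t-tests; a rule that they follow a significant ANOVA.

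Read literally, the condition cannot be satisfied.

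**2. What happens if unadjusted paired t-tests are used between conditions?**

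Inputs: two-sided alpha 0.05 (9.4.1); *n* = 15 completers and 20 recruited per phase (9.2); three exercise conditions and two cannabis-at-rest conditions per phase (9.4.1 and the Schedule of Activities). The plan does not define the family, so the pair counts below are inferred from the schedule.

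- Exercise-only endpoints: 3 × 2 / 2 = 3 pairs.
- Endpoints recorded at every visit: 5 × 4 / 2 = 10 pairs. Of these, 3 are exercise-exercise, 1 is rest-rest, and 2 × 3 = 6 are rest-exercise.
- For heart rate and rate-pressure product, the 6 rest-exercise pairs compare rest after cannabis with 20 minutes of maximal cycling. They cannot sensibly be null, and 9.1 itself predicts that exercise raises heart rate. A false positive is then possible in 3 + 1 = 4 pairs.

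Chance of at least one p < 0.05 with no true difference in the pairs counted (40,000 simulated data sets, normal data, equal correlation between conditions):

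| Pairs that are null | *n* = 15 | *n* = 20 |
|---|---|---|
| 3 (exercise conditions) | 12.6% | 12.3% |
| 4 (heart rate, rate-pressure product) | 16.9% | 16.5% |
| 10 (all pairs) | 30.1% | 29.0% |

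Two hand checks:

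- For three independent tests the figure would be 1 − 0.95³ = 14.3%. Pairs that share a condition are correlated, which brings it down to about 12.5%.
- The rest-rest pair shares no condition with the exercise pairs, so at *n* = 15 the four-pair figure should be near 1 − (1 − 0.126)(1 − 0.05) = 17.0%, as simulated.

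With Bonferroni the per-test level is 0.05/3 = 0.0167 for 3 pairs (simulated error about 4.5%) and 0.05/10 = 0.005 for 10 pairs (about 4.2%). For 4 pairs it is 0.05/4 = 0.0125, and the familywise error cannot exceed 4 × 0.0125 = 5%.

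If the unadjusted t-tests were run only after a significant omnibus F-test, the error with all conditions equal would be about 5%. The plan does not state that order.

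**The case against.** The strongest reply is that this is loose wording and the intention is clear. The same sentence names Bonferroni as the method for comparing pairs of means, and many readers would take *interactions* to mean a significant ANOVA effect. It could also be left over from a two-factor model: the stroke-volume hypothesis in 9.1 is a cannabis-by-exercise interaction, and perceived exertion is rated every 2 minutes (8.1). This stands as far as it goes. A reader might infer that the correction will certainly never be applied and that unadjusted t-tests are all that remain. The documents do not support that: the omnibus F-test is still there, and the intended meaning is open. But each charitable reading also needs a change of text, and none gives the paired t-tests a role.

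Second, the plan does not say that the t-tests compare all pairs of conditions. Heart rate and blood pressure are monitored before and during inhalation (4.1), and no visit is a cannabis-free rest condition, so pre- versus post-consumption comparison is a natural use. That stands, and it makes the error rates above conditional.

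Third, a reader might apply the 30% figure to every endpoint recorded at all visits. It needs all ten pairs to be null. Diastolic pressure, predicted to be unchanged throughout, is the one endpoint in that group whose stated hypothesis fits. For heart rate and rate-pressure product, about 17% is the relevant figure.

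**Conclusion.** The rule is wrong as written, in both documents and in each place it appears: its trigger is a term that the specified model does not have. Nothing elsewhere supplies a working trigger, an adjustment for the paired t-tests or an order of testing. What was meant cannot be settled from the text.

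If between-condition conclusions were drawn from unadjusted paired t-tests, the chance of a false positive per endpoint and phase would be about 12-13% with three exercise conditions and about 17% for heart rate and rate-pressure product, against a nominal 5%. It would reach about 30% only under a complete null across five conditions. These figures assume that use of the t-tests, the inferred pair counts, and normal, equally correlated data.

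The defect is confined to secondary endpoints, which 9.4.3 analyses separately from the primary ones. It does not touch the sample size, the primary analysis or safety. It should be corrected before the secondary data are analysed, because a choice of p-value made afterwards would depend on the data.

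**What to change.** In Protocol 9.4.1 and 9.4.3 and the matching SAP sections:

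1. Replace *significant interactions* with *a significant condition effect*. Where an interaction is the hypothesis, as for stroke volume, specify a two-factor model instead (condition by time, or cannabis by exercise). Because the schedule has no cannabis-free resting visit, state which measurement is the resting reference.
2. List the between-condition contrasts for each phase: each cannabis-plus-exercise condition against exercise alone; the two cannabis-plus-exercise conditions against each other; and, for endpoints recorded at rest, the two cannabis-at-rest conditions against each other. Apply Bonferroni or Holm within that list.
3. Keep paired t-tests only for the stated pre- versus post-consumption hypotheses, such as the predicted rises in heart rate and systolic pressure. List them in advance and include them in the adjustment. Removing all paired t-tests would leave those hypotheses without a test.
4. Reconcile 4.1 with 8.1 on whether blood pressure, heart rate and rate-pressure product are analysed at rest visits, since this decides whether there are three or four contrasts.

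The cost is wording plus a stricter per-contrast threshold: 0.05/3 = 0.0167 for three contrasts, 0.05/4 = 0.0125 for four, and lower if pre-post tests join the family. No visit, measurement or sample size changes.
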